clinically meaningful and consistent with previous trials of renal denervation in a similar population¹. An observed difference between groups of 5 mmHg with an observed SD as high as 11.2 mmHg per group would be considered statistically significant at a two-sided alpha level of 0.05.

Endpoints and Planned Statistical Analysis

The following populations are defined for analysis:

The Intent-to-Treat (ITT) Analysis Set will include all subjects who were randomized regardless of whether treatment was received. Subjects will be analyzed according to their randomized treatment group, irrespective of treatment received.

The Safety Analysis Set will include all subjects who received treatment. Subjects will be analyzed according to the actual treatment received, irrespective of treatment assignment.

The Per-Protocol (PP) Analysis Set will include subjects with no important protocol deviations. Subjects will be analyzed according to the actual treatment received.

Primary efficacy endpoint

The primary efficacy endpoint is defined as the change in mean 24-hour ambulatory SBP from baseline to 8 weeks post-treatment. This will be summarized and compared between the 2 treatment groups using the independent two-sample t-test.

Secondary efficacy endpoints:

- Change in mean 24-hour, daytime, (07:00 to 21:59), and nighttime (22:00 to 06:59) ambulatory SBP and DBP from baseline to time points post-treatment.
- Change in mean office SBP and DBP from baseline to time points post-treatment.
- Percentage of subjects controlled to target blood pressure values.
- Use of antihypertensive medication(s) from time of procedure to 8 weeks post-treatment (emergency use medication).
- Use of antihypertensive medication(s) (including increases/decreases) from 8 weeks to 6 months and 1-year post-treatment (titrated according to standardized formula to maintain a target SBP of <140 mmHg and ≥90 mmHg).
- Compliance with not taking antihypertensive medications through 8 weeks post-treatment.

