Appendix I Proposed Structured Drug Titration

After 8 weeks post-treatment, subjects may take antihypertensive medications to maintain a target office SBP of <140 mmHg and ≥ 90 mmHg (based on a mean of 3 measurements). The titration regimen provided in the following table should be followed if possible.

Step (Target SBP <140 mmHg and ≥ 90 mmHg) ¹	Drug	Treatment Score
0 (not needed)	None	0
1 (if needed)	CCB: mid-dose	1
2 (if needed)	ACE inhibitor or ARB: full dose	2
3 (if needed)	Hydrochlorothiazide 12.5 mg	3
4 (if needed)	Hydrochlorothiazide 25 mg	4
5 (if needed)	CCB: increase to full dose	5
6 (if needed)	Spironolactone or beta-blocker or clonidine	6
7 (if needed)	Spironolactone or beta-blocker or clonidine	7
8 (if needed)	Spironolactone or beta-blocker or clonidine	8

Abbreviations: ACE = angiotensin-converting enzyme; ARB = angiotensin receptor blocker; BP = blood pressure; CCB = calcium channel blocker; SBP = systolic blood pressure.

1 There will usually be 2 to 3 weeks between steps. If the target is reached, there are no further steps even if BP fluctuates above the target. For Steps 6, 7, and 8, the choice of drug and dose is at the investigator's discretion. If initial systolic BP is ≥ 160 mmHg, Steps 1 and 2 can be combined. Fixed-combination drug products can be used to decrease pill burden.

Source: Weber MA, Kirtane A, Mauri L, et al. Renal denervation for the treatment of hypertension: making a new start, getting it right. *J Clin Hypertens* 2015;17(10):743-50.

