5.5.2. Secondary Efficacy Endpoints

5.5.2.1. Change in Mean 24-hour, Daytime, and Nighttime Ambulatory SBP and DBP from Baseline to Time Points Post-Treatment.

The mean change in ambulatory blood pressures at all collected time points will be reported with 95% CIs as described in Section 5.6. These analyses will be conducted in the ITT and PP analysis sets.

The sensitivity analyses as proposed in Section 5.4.1 for the primary mean 24-hour SBP will be additionally conducted for the 8-week daytime and nighttime SBP.

5.5.2.2. Change in Mean Office SBP and DBP from Baseline to Time Points Post-Treatment. The mean change in office blood pressures at all collected time points will be reported with 95% CIs as described in Section 5.6. These analyses will be conducted in the ITT and PP analysis sets.

The sensitivity analyses as proposed in Section 5.4.1 for the primary mean 24-hour SBP will be additionally conducted for the 8-week office SBP.

5.5.2.3. Percentage of Subjects Controlled to Target Blood Pressure Values.

The number and percent of patients controlled to target office blood pressure of <140 and >90 mmHg will be summarized by treatment group and compared via Fisher's Exact test. These analyses will be conducted in the ITT and PP analysis sets.

5.5.2.4. Use of Antihypertensive Medication(s) from Time of Procedure to 8 weeks Post-Treatment (Emergency Use Medication).

The mean change in the number of antihypertensive medications will be summarized as described in Section 5.7 along with 95% CIs for the mean change in number of medications. The addition of new antihypertensive drugs will be considered an intensification of the antihypertensive regimen. Discontinuation of one or more of the baseline antihypertensive medications without an increase in dose of remaining drugs or addition of new drugs will be considered a reduction in antihypertensive drug regimen.

Antihypertensive dose titration will be scored according to the protocol as defined in the tables below. The mean treatment score will be reported by treatment group and the groups compared via Fisher's Exact test. These analyses will be conducted in the ITT and PP analysis sets.

Step (Target SBP <140 mmHg and ≥90 mmHg)¹	Drug	Treatment Score ²
0 (not needed)	None	0
1 (if needed)	CCB: mid-dose	1
2 (if needed)	ACE inhibitor or ARB: full dose	2
3 (if needed)	Hydrochlorothiazide 12.5 mg	3
4 (if needed)	Hydrochlorothiazide 25 mg	4
5 (if needed)	CCB: increase to full dose	5

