6 (if needed)	Spironolactone or beta-blocker or clonidine	6
7 (if needed)	Spironolactone or beta-blocker or clonidine	7
8 (if needed)	Spironolactone or beta-blocker or clonidine	8

Abbreviations: ACE = angiotensin-converting enzyme; ARB = angiotensin receptor blocker; BP = blood pressure; CCB = calcium channel blocker; SBP = systolic blood pressure.

- 1. There will usually be 2 to 3 weeks between steps. If the target is reached, there are no further steps even if BP fluctuates above the target. If initial systolic blood pressure (SBP) is ≥160 mmHg, Steps 1 and 2 can be combined. Fixed-combination drug products can be used to decrease pill burden.
- 2. The treatment score will be used for the purpose of the statistical analysis.

Source: Weber et al. 2015

5.5.2.5. Use of Antihypertensive Medication(s) (including Increases/Decreases) from 8 weeks to 6 months Post-Treatment (Titrated According to Standardized Formula to Maintain a Target SBP of <140 mmHg and ≥90 mmHg).

The mean change in the number of antihypertensive medications will be summarized as described in Section 5.7 along with 95% CIs for the mean change in number of medications. The addition of new antihypertensive drugs will be considered an intensification of the antihypertensive regimen. Discontinuation of one or more of the baseline antihypertensive medications without an increase in dose of remaining drugs or addition of new drugs will be considered a reduction in antihypertensive drug regimen.

The mean treatment score will be reported by treatment group and the groups compared via Fisher's Exact test. These analyses will be conducted in the ITT and PP analysis sets.

5.5.2.6. Compliance with Not Taking Antihypertensive Medications Through 8 weeks Post-Treatment. The number and percent of patients in whom no antihypertensive medications are detected according to urine compliance results will be summarized by treatment group and compared using Fisher's Exact test. Subjects who meet the protocol defined criteria for antihypertensive drug treatment and receive treatment within 8 weeks will be excluded from the analysis. These analyses will be conducted in the ITT and PP analysis sets.

5.5.2.7. Use of Antihypertensive Medication(s) according to Defined Daily Dose.

In addition to the protocol specified analyses as described above, prescribed medications will be summarized according to the sum of the defined daily dose (DDD) in order to assess and

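### The SAP's intensification and reduction labels do not measure increases and decreases in antihypertensive treatment, though dose-sensitive summaries elsewhere limit the effect

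*SAP*

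**What the plan says.** The protocol synopsis lists as a secondary efficacy endpoint "Use of antihypertensive medication(s) (including increases/decreases) from 8 weeks to 6 months and 1-year post-treatment". The matching SAP section, 5.5.2.5, is titled "Use of Antihypertensive Medication(s) (including Increases/Decreases) from 8 weeks to 6 months Post-Treatment" and stops at 6 months.

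SAP 5.5.2.4 (emergency use up to Week 8) and 5.5.2.5 give the same two definitions:

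- Intensification: "The addition of new antihypertensive drugs will be considered an intensification of the antihypertensive regimen".
- Reduction: "Discontinuation of one or more of the baseline antihypertensive medications without an increase in dose of remaining drugs or addition of new drugs".

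Dose enters only as a condition that cancels a reduction.

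The titration table (Protocol Appendix I, repeated in SAP 5.5.2.4) has eight steps above Step 0. Step 3 is "Hydrochlorothiazide 12.5 mg", Step 4 is "Hydrochlorothiazide 25 mg" and Step 5 is "CCB: increase to full dose". Each step scores one more point than the step before.

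The two sections also report the change in number of drugs and the mean treatment score. SAP 5.5.2.7 adds a summary by DDD.

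**The concern.** The labels are the only place where the SAP says what counts as an increase or a decrease, and they count drugs, not treatment intensity. After Week 8 both arms may be titrated towards the same office systolic target, so the amount of drug needed is part of how any later blood-pressure difference is read. A label that ignores dose can disagree with the treatment score for the same subject. A label that depends on an undefined baseline may also be unable to record one of the two directions that the endpoint names.

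**Working it through.** The plan states no figure to reproduce here. The check applies the SAP wording to the titration table and then to each possible meaning of baseline.

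**1. One-step moves.** Inputs: the titration table and the two definitions above. Protocol Appendix I leaves drug and dose at Steps 6 to 8 to the investigator; I assume that each adds a drug.

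| Move to step | What changes | Drug count | Score | Label |
|---|---|---|---|---|
| 1 | CCB added | 1 | 1 | intensified |
| 2 | ACE inhibitor or ARB added | 2 | 2 | intensified |
| 3 | thiazide added | 3 | 3 | intensified |
| 4 | thiazide dose raised | 3 | 4 | none |
| 5 | CCB dose raised | 3 | 5 | none |
| 6 | drug added | 4 | 6 | intensified |
| 7 | drug added | 5 | 7 | intensified |
| 8 | drug added | 6 | 8 | intensified |

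Two of the eight one-step moves have no label.

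**2. All upward moves.** Nine levels give 9 × 8 / 2 = 36 upward moves. Three add no drug: 3 to 4, 4 to 5 and 3 to 5. From Step 0, all 8 destinations add at least one drug, so none is missed.

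**3. Where subjects start.** The notes to Protocol Figure 1 put subjects on 0 antihypertensive drugs from Week -4. Table 1, footnote 17, keeps them there until the Week 8 visit is completed, emergencies apart. In the interval of SAP 5.5.2.5, nearly everyone therefore starts at Step 0. A subject found at Step 4 or 5 by the table has already been labelled intensified. The three unlabelled moves matter only if change is measured from a later visit. An example is a subject at Step 3 at 6 months and Step 5 at 1 year: score +2, drug count +0, no label.

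**4. Reductions if baseline is the last value before the procedure.** SAP 5.2.1 defines baseline this way for every variable. By design that value is 0 drugs, so there is no baseline drug to stop, and 0 of the 36 downward moves is a reduction. If the rule instead referred to the drugs held at the start of the move, 36 - 3 = 33 downward moves would qualify. The three dose-only step-downs (5 to 4, 4 to 3, 5 to 3) would still be missed.

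**5. If baseline means the 0 to 2 drugs at enrollment.** SAP 5.4.1 hints at this reading: it uses the number of medications at baseline as an imputation covariate, which would be nearly constant at 0 under the other reading. Applying the rule to constructed cases:

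- Same drug resumed at a higher dose: no label.
- Same drug resumed at a lower dose: no label.
- One drug at enrollment, a different single drug later: intensified, although the count is 1 and 1.
- Two drugs at enrollment, one later at a higher dose: no label.

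The labels fail to track increases and decreases on either reading, in different ways.

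**The case against.** The strongest reply is that little depends on these labels, and much of it stands. Subjects who follow the table from 0 drugs are labelled intensified as soon as they start. The treatment score rises at Steps 4 and 5, and a footnote to the SAP table says that the score serves the statistical analysis. The DDD summary captures total consumption. The visible SAP text specifies no percentage intensified and no between-arm test of it, and the table shells that might do so are not available. Secondary endpoints are supportive, and SAP 5.2.1 disclaims formal hypothesis testing.

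It can also be said that the SAP calls an added drug an intensification without saying that nothing else is one. That is literally true, but it leaves a dose increase undefined, and the reduction rule shows that the authors had dose in view.

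The score and the DDD summary do not repair the labels. Neither is used to define an increase or a decrease. The test named for the mean score is Fisher's exact test, which does not compare means. SAP 5.5.2.7 gives the DDD summary no time interval and no test, and no table title in SAP section 9 names it.

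Two further cautions are fair. The count of two dose-only steps assumes that Steps 6 to 8 each add a drug; if one is used to raise an existing dose, more steps go unlabelled. The table is to be followed where possible, so the score alone cannot classify every regimen.

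**Conclusion.** The labels do not measure the endpoint as stated. Dose-only changes have no label, a one-for-one substitution is labelled intensification, and under the SAP's own general definition of baseline no reduction can be recorded. The reference visit and the unit of counting (subject or change) are also unstated.

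The consequence is modest: a descriptive label within a supportive secondary endpoint may mislead or contradict the score. The primary analysis is unaffected.

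A reader might infer that a quarter of escalation is lost (2/8 = 25%), that each misclassified subject moves an arm's rate by 2.2 percentage points (1/45), or that a between-arm difference is diluted. The documents support none of these as an effect on a result. The 25% counts adjacent steps, not subjects. The 2.2 points convert one subject into a rate that the plan does not say it will compare. Subjects starting from 0 drugs are labelled at their first step. Nor can a reader conclude that dose information is lost from the trial, since two other planned summaries carry it.

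**What to change.** In SAP 5.5.2.5, extended to 1 year to match the current protocol, replace the two definitions with one rule. Classify each subject as increased, decreased or unchanged by the sign of the net change in treatment score between two named visits. Use summed DDD instead for regimens outside the titration table and for drugs taken at enrollment. Classify substitutions by the same net change.

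State whether the reference is the enrollment regimen or the Week 8 regimen. The choice matters: measured from Week 8, a subject on 0 drugs cannot show a decrease, so that direction would be nearly empty. Also state that the subject is the unit of counting.

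In SAP 5.5.2.4, which covers emergency use before the titration table applies, drop the labels and report DDD or any use only.

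The cost is SAP wording and minor programming. Antihypertensive drugs are recorded from consent to the 2-year visit (Protocol Table 1, footnote 24), and SAP 5.13 already lists their doses.

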- Significant acute (post-procedural) renal artery stenosis (>60% diameter stenosis) as indicated by the renal angiogram post renal denervation, and confirmed by the angiography core laboratory, which led to one of the following: (i) acute kidney injury per modified Risk, Injury, Failure, Loss of kidney function, and End-stage kidney disease (RIFLE) definition, as confirmed by renal function blood test, or (ii) percutaneous intervention.
- Hypertensive crisis (hypertensive emergency only)
- Hypotensive crisis
- Symptomatic hypotension that required a change in antihypertensive medications, or medications to increase blood pressure (e.g. persistent syncope, lightheadedness)
- Changes in eGFR from baseline to 8 weeks, 6 months, and 1-year post-treatment.
- Decreases in eGFR >25% from baseline to 8 weeks, 6 months, and 1-year post-treatment.
- Rate of adverse events (serious and non-serious), peri-procedurally, at discharge, and at each of the follow-up time points.
- Device success (defined as the ability to insert the Peregrine Catheter into the lumen of the renal artery [target vessel], deploy the guide tubes inside the renal artery, deploy the needles through the arterial wall, deliver the intended dose of alcohol, retract the needles and the guide tubes back in the catheter, and remove the catheter from the access site without any related complications or events)
- Procedure success (defined as device success with freedom from peri-procedural MAEs).

The percentage of subjects with any MAE through 30 days post-treatment will be displayed by treatment group. The relative risk will be displayed with 95% CIs. The 2 groups will be compared using Fisher's exact test.

Other safety endpoints will be summarized as frequencies and percentages. Relative risks and 95% CIs will be computed. Analysis of all safety endpoints will be conducted using the Safety Analysis Set.

Table 1 Schedule of Study Assessments (Main Study)

Period	Scrn Period	Run-In Period ¹			In-Hospital Period		Follow-Up Period					ET ²	
Visit Time Point	Up to Wk -8	Wk -4	Wk -2	Wk -1 (Baseline)	D 0 ³	D 1	D 2 to D 4 (48-96 h) ⁴	Wk 4	Wk 8	Mth 3	Mth 6	Yr 1 and 2	
Visit Window			+/-4 D	+/-2 D				+/-7 D	+/-7 D	+/-2 Wk	+/-4 Wk	+/-8 Wk	
Informed consent	X												
Eligibility check	X			X									
Demographic data	X												
Medical history	X												
Office BP pressure ⁵	X		X	X				X	X	X	X	X	X
24-hour ABPM ⁶				X ⁷					X		X		X ⁸
MRA/CTA ⁹	X ¹⁰											X ¹¹	

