5.2. General Considerations

5.2.1. General Methods

Two unblinded team members (either two statisticians or a statistician and a statistical programmer) will be assigned for all analyses. This will allow for discussion of output and direct QC of statistical programming on the exact same dataset.

In general, continuous variables will be summarized with descriptive statistics (n, mean, SD, range, median, and interquartile range). The difference between groups will be presented and the normal approximation will be used to calculate two-sided 95% confidence intervals (CIs). Change from baseline, when relevant, will be computed as the paired mean difference and 95% CI of the mean difference at each time point.

For all continuous primary and secondary blood pressure endpoints, changes over time will be additionally explored in mixed effects repeated measures analyses, including the values at all time points.

Categorical variables will be summarized as frequencies and percentages. Relative risks and 95% CIs will be computed.

All statistical analyses will be performed using SAS® Version 9.4 or higher (SAS Institute, Cary, NC 27513, USA).

For each variable, the baseline value will be defined as the last value collected before the procedure.

There will be no formal hypothesis testing conducted in the study. Ninety-five percent CIs, when presented, are intended to be descriptive in nature only. For binary variables, CIs will be calculated via exact binomial methods. For continuous variables, the CI of the mean will be constructed using the normal approximation.

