An additional exploratory analysis will be conducted, which combines the treatment failures (subjects receiving rescue medication) with the continuous 24-hour ambulatory SBP measurement in a hierarchical fashion using the approach described in Finkelstein and Schoenfeld (1999) and later adapted to the Win Ratio by Pocock (2012). Using this approach, each subject is compared to every other subject first as to whether or not the subject received rescue medication. If both subjects did or did not receive rescue medication (i.e., there is a tie), then the subjects will have their change in 24-hour ambulatory SBP at 8 weeks compared. A score of -1 will be assigned to a loss and a score of +1 will be assigned to a win. For example:

- If Subject A receives rescue medication within 8 weeks and Subject B does not, Subject A loses (score -1), and Subject B wins (score +1)
- If neither receive rescue medication within 8 weeks, then if Subject A has a larger reduction in 24-hour ambulatory SBP at 8 weeks compared to Subject B, then Subject A wins (score +1) and Subject B loses (score -1).

After all between-subject comparisons have been performed, scores will be summed to obtain a cumulative score for each subject, and the scores between treatment groups will be compared using the Mann-Whitney U test. The resulting p-value will be presented. The win ratio will also be presented. It is calculated as number of "wins" divided by the number of losses out of all comparisons of intervention to sham subjects.

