5.5.1.2. Changes in eGFR from Baseline to 8 weeks and 6 months Post-Treatment

The change in eGFR will be summarized between baseline and 8 weeks and baseline and 6 months. Changes in eGFR at 8 weeks and 6 months will be compared between groups using the independent two-sample t-test. These analyses will be conducted in the Safety Analysis Set.

5.5.1.3. Decreases in eGFR >25% from Baseline to 8 weeks and 6 months Post-Treatment
The number and percent of patients with greater than a 25% reduction in eGFR will be summarized at 8 weeks and 6 months. Groups will be compared using Fisher's Exact test. These analyses will be conducted in the Safety Analysis Set.

5.5.1.4. Rate of Adverse Events (Serious and Non-Serious), Peri-Procedurally, at Discharge, and at Each of the Follow-up Time Points.

Coded AEs will be summarized at each follow-up time period (any events occurring prior to and including the follow-up time) and overall according to system organ class (SOC) and Preferred Term (PT) by treatment group as described in Section 5.8.1 below.

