Table 14.2.2-3 24-Hour Ambulatory Blood Pressure at 8 weeks, 6 months and 1 Year, by baseline daytime ambulatory SBP >140 mmHg and DBP <90 mmHg - ITT Analysis Set

Table 14.2.2-4 Exploratory analysis of 24-Hour Systolic Ambulatory Blood Pressure at 8 weeks HIERARCHICAL MODEL - ITT Analysis Set

Table 14.2.2-5 Exploratory analysis of 24-Hour Systolic Ambulatory Blood Pressure at 8 weeks HIERARCHICAL MODEL - PP Analysis Set

Table 14.2.3-1 Daytime Ambulatory Blood Pressure at 8 weeks, 6 months and 1 Year ALL

AVAILABLE DATA - ITT Analysis Set

Table 14.2.3-2 Daytime Ambulatory Blood Pressure at 8 weeks, 6 months and 1 Year ALL AVAILABLE DATA - PP Analysis Set

Table 14.2.3-3 Daytime Ambulatory Blood Pressure at 8 weeks, 6 months and 1 Year, by baseline daytime ambulatory SBP >140 mmHg and DBP <90 mmHg - ITT Analysis Set

Table 14.2.3-4 Daytime Ambulatory Systolic Blood Pressure at 8 weeks SENSITIVITY ANALYSES – ITT Analysis Set

Table 14.2.3-5 Daytime Ambulatory Systolic Blood Pressure at 8 weeks SENSITIVITY ANALYSES – PP Analysis Set

Table 14.2.4-1 Nighttime Ambulatory Blood Pressure at 8 weeks, 6 months and 1 Year ALL AVAILABLE DATA - ITT Analysis Set

Table 14.2.4-2 Nighttime Ambulatory Blood Pressure at 8 weeks, 6 months and 1 Year ALL AVAILABLE DATA - PP Analysis Set

Table 14.2.4-3 Nighttime Ambulatory Blood Pressure at 8 weeks, 6 months and 1 Year, by baseline daytime ambulatory SBP >140 mmHg and DBP <90 mmHg - ITT Analysis Set

Table 14.2.4-4 Nighttime Ambulatory Systolic Blood Pressure at 8 weeks SENSITIVITY ANALYSES – ITT Analysis Set

Table 14.2.4-5 Nighttime Ambulatory Systolic Blood Pressure at 8 weeks SENSITIVITY ANALYSES – PP Analysis Set

Table 14.2.5-1 Office Blood Pressure at 8 weeks, 6 months, 1 Year and 2 Years - ITT Analysis Set

Table 14.2.5-2 Office Blood Pressure at 8 weeks, 6 months and 1 Year ALL AVAILABLE DATA - PP Analysis Set

Table 14.2.5-3 Office Blood Pressure at 8 weeks, 6 months and 1 Year, by baseline daytime ambulatory SBP >140 mmHg and DBP <90 mmHg - ITT Analysis Set

Table 14.2.5-4 Office Blood Pressure at 8 weeks SENSITIVITY ANALYSES – ITT Analysis Set

Table 14.2.5-5 Office Blood Pressure at 8 weeks SENSITIVITY ANALYSES – PP Analysis Set

Table 14.2.6-1 Antihypertensive Medication Use EMERGENCY USE MEDICATIONS - ITT Analysis Set

Table 14.2.6-2 Antihypertensive Medication Use EMERGENCY USE MEDICATIONS – PP Analysis Set

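### SAP 5.5.2.4 and 5.5.2.5 report the mean of an ordered 0–8 treatment score but compare the arms with Fisher's exact test, which, with no category split stated, tests neither the mean nor the order

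*SAP*

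**What the plan says.** The sentence "The mean treatment score will be reported by treatment group and the groups compared via Fisher's Exact test" stands in both SAP 5.5.2.4 (procedure to 8 weeks) and SAP 5.5.2.5 (8 weeks to 6 months). The score comes from the titration table in 5.5.2.4, which follows Appendix I of the protocol: steps 0 to 8, each scored with its own step number. Footnote 2 to that table makes the score itself the analysis variable: "The treatment score will be used for the purpose of the statistical analysis".

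Neither section says how the score would be put into categories. The table titles in SAP section 9 do not say either, for example "Table 14.2.6-1 Antihypertensive Medication Use EMERGENCY USE MEDICATIONS - ITT Analysis Set". The nearest split, in SAP 5.7, is 0 to 3 versus more than 3 and applies to the number of medications, not the score.

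For continuous variables, SAP 5.2.1 already sets the summary: "The difference between groups will be presented and the normal approximation will be used to calculate two-sided 95% confidence intervals (CIs"). The protocol synopsis names no test for the treatment score.

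**The concern.** Fisher's exact test asks whether category frequencies differ between arms. On a 2×9 table it treats the nine scores as unordered labels. A p-value from it therefore does not test the reported mean, and it does not use the fact that step 5 is more treatment than step 1. If a 2×2 test was intended, the cut-point is missing and the result depends on it.

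Elsewhere the documents match test to variable:

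- Yes/no outcomes get Fisher's test. For 30-day major adverse events the protocol says "The 2 groups will be compared using Fisher's exact test", and SAP 5.5.2.6 plans that subjects in whom "no antihypertensive medications are detected according to urine compliance results will be summarized by treatment group and compared using Fisher's Exact test".
- A continuous outcome gets a t-test: "Changes in eGFR at 8 weeks and 6 months will be compared between groups using the independent two-sample t-test" (SAP 5.5.1.2).
- A per-subject score gets a rank test: "the scores between treatment groups will be compared using the Mann-Whitney U test" (SAP 5.4.1, hierarchical analysis).

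The treatment score is the exception. After 8 weeks both arms may be titrated to the same office SBP target, so part of any treatment effect may appear as lower drug burden rather than lower pressure. The comparison in 5.5.2.5 helps the reader interpret the 6-month pressures, and its p-value would be printed beside a mean difference and CI that it does not test.

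**Working it through.** **The plan's own figure.** The documents give no power or expected distribution for the treatment score. The only power figure concerns the primary endpoint (80% for 5.1 mmHg, SD 8, two-sided alpha 0.05, 80 evaluable). With 40 per arm the noncentrality is 5.1 / (8 × √(2/40)) = 5.1 / 1.789 = 2.85. On 78 degrees of freedom the power is 80.4%, so the figure reproduces with 40 per arm, the size used below.

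**Constructed example.** Counts for scores 0 to 8:

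- Arm A: 8, 6, 6, 5, 5, 4, 3, 2, 1 (sum of scores 113, mean 113/40 = 2.825, variance 5.276)
- Arm B: 14, 8, 6, 4, 3, 2, 2, 1, 0 (sum 73, mean 73/40 = 1.825, variance 3.943)

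The difference is 1.00 and SE = √((5.276 + 3.943)/40) = 0.480. By the normal rule of SAP 5.2.1 the 95% CI is 1.00 ± 1.96 × 0.480 = 0.06 to 1.94. On the same data:

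- Welch t-test: p = 0.041
- Wilcoxon rank-sum: p = 0.042
- Fisher on the 2×9 table (1,000,000 Monte Carlo draws): p = 0.83
- Fisher, any drug versus none (32/40 versus 26/40): p = 0.21

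**Relabelling.** Replace scores 0–8 by 4, 2, 7, 3, 5, 0, 1, 8, 6. Both sums become 151 and both means 151/40 = 3.775. Wilcoxon p becomes 1.0. The 2×9 counts are the same up to column order, so Fisher's p stays at 0.83. It is the same whether the means differ by 1.00 or by 0.

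**Cut-point.** If a 2×2 Fisher test was meant, cuts at ≥1, ≥2, ≥3, ≥4 and ≥5 give p = 0.21, 0.12, 0.11, 0.14 and 0.25 on these data. On a second constructed data set (means 2.88 and 1.75) they give 0.210, 0.071, 0.069, 0.078 and 0.139. The choice matters and is not stated.

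**Simulation.** 4,000 trials per setting, 40 per arm, two-sided 0.05. All score distributions are assumed. Latent normal means a normal variable with SD 2, rounded and clipped to 0–8, with mean 2 versus 1.25, 1, 0.75 or 0.5. In the other settings the share at score 0 and the geometric decay of the nonzero scores are set separately. Figures are percentages, given as the range over settings.

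| Assumed pattern | Power: Fisher 2×9 | Power: Fisher any vs none | Power: Wilcoxon | CI excludes 0, Fisher 2×9 p > 0.05 | CI excludes 0, Wilcoxon p > 0.05 |
|---|---|---|---|---|---|
| Latent normal shift (4 settings) | 16.9–58.5 | 17.7–64.0 | 35.2–86.5 | 23.6–33.1 | 2.4–4.4 |
| Zero share and level both shift (4) | 21.1–35.2 | 20.7–35.4 | 45.2–67.4 | 33.6–40.7 | 7.2–14.5 |
| Only zero share differs (4) | 25.3–56.4 | 37.1–74.6 | 36.4–71.0 | not tabulated | not tabulated |
| Only level among drug users differs (3) | 44.1–51.6 | 2.4–3.0 | 35.9–53.0 | 26.2–28.5 | 21.5–26.0 |

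In null settings (3,000 trials each) rejection was 4.7–5.4% for Fisher 2×9, 2.3–3.6% for binary Fisher and 4.4–5.8% for Wilcoxon, so no test is invalid.

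A separate simulation under proportional odds (common odds ratio 2.5 to 3, two assumed distributions, 40 or 45 per arm) gave power of 30–51% for Fisher 2×9, 37–64% for binary Fisher, 55–83% for Wilcoxon and 49–81% for the t-test.

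**The case against.** **The table shells were not available.** The SAP is meant to be read with them. If they define a split such as any drug versus none, Fisher's test is appropriate for that split. This stands as a limit. Even so, it would not test the reported mean, and a split should be stated in the text that orders the comparison.

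**Loose drafting.** Both sections also define intensification and reduction of the regimen, and Fisher's test may have been meant for such categories. That is plausible, but the sentence attaches the test to the score.

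**Section 5.5.2.4 differs.** Before 8 weeks only emergency drugs are allowed, so most scores should be 0 and the comparison is close to any versus none. This is right: the 24–41% figure describes 5.5.2.5. With sparse use the mismatch shrinks but remains. The CI excluded 0 with Fisher 2×9 not significant in about 15–17% of trials in the sparse settings tried, against about 2% for Wilcoxon. With binary Fisher it was about 6–10%, assuming 10–25% versus 2–5% on drug.

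**Wilcoxon does not test the mean either, and is not always stronger.** Both are true. The last two rows of the table show where a Fisher test equals or beats it, and in the level-only settings Wilcoxon disagrees with the CI nearly as often. The reason to prefer it is that it uses the order of the score and matches the SAP's own practice in 5.4.1. A t-test on the mean would also be coherent.

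**Little depends on it.** Secondary endpoints are supportive, no formal testing is planned, and drug burden is also shown by number of medications, class and defined daily dose. This limits the weight of the point but does not remove it, since the SAP still orders this comparison.

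**Conclusion.** The concern holds and should be corrected. As written, both sections pair the mean of an ordered score with a test that ignores its values and order, and no section or table title supplies a split that would change that.

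The invariance to relabelling is a mathematical fact and needs no assumption. The size does need assumptions, because the documents give no score distribution. Where scores shift between arms, the CI and Fisher 2×9 disagree in 24–41% of trials, against 2–15% for Wilcoxon, and Wilcoxon power is 18–32 points above Fisher 2×9. These figures do not carry over to every pattern, so the defect is the mismatch and not a general loss of power. Type I error is sound, and the primary endpoint and its conclusion are untouched.

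**What to change.** In SAP 5.5.2.4 and 5.5.2.5 replace the sentence with wording to this effect: *The treatment score will be compared between groups with the Wilcoxon rank-sum test and presented with the difference in means and its 95% CI as set out in Section 5.2.1.* Keep Fisher's exact test only for a binary split named in the text, such as any antihypertensive drug versus none, reported with counts and percentages. If the table shells already contain such a split, state it in both sections.

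The cost is one sentence in each of two sections and one line of code. No new data are needed, and the change conflicts with none of the protocol text supplied.
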